### **E.15. On-Site Audits**

At any time, representatives of the sponsor's steering committee may schedule a visit of a study site during or after completion of the study. Purpose of such a visit is to conduct an audit of the study for ensuring compliance with regulatory guidelines and subject privacy. Such an audit visit would require access to all study records, including source documents, for review and comparison to the CRFs. The site lead investigator and study-site personnel would need to be made available for query during each audit visit conducted by the sponsor. Similar auditing procedures may also be conducted by agents of any regulatory body, either as part of a national GCP compliance program or to review the results of this study in support of a regulatory submission. The site investigator should immediately notify the sponsor if contacted by a regulatory agency concerning an upcoming inspection.

### **E.16. Statistical Analysis**

The sample size of 100 has been selected based on feasibility of completion across the 7 study sites, and as larger pilot expansion of clinical practice feasibility. The intent is to enroll 100 subjects (70 unipolar/ 30 bipolar) over 4 sites which would estimate 25 subjects per site. Given potential delays in obtaining IRB approval, some sites may over-recruit. For most data elements, descriptive statistics such as means and standard deviations will be reported. Comparisons of means before and after treatment will be based on *t* tests. Statistical support will be provided from designated psychiatry and psychology department statistician time.

For Aim 1, we will compare baseline WBC markers of impaired cellular energy regulation (described above, see §B.5.c) between remitters and non-remitters using ANCOVA models adjusted for study site, age, and sex. Analyses comparing the baseline biomarkers of responders and non-responders will be performed using similar models, and the association of biomarkers with percent change in MADRS score will be evaluated using linear regression mixed models.

For Aim 2, similar analyses will be performed comparing the other biomarker measures between remitters and non-remitters (and responders and non-responders), and testing for association between percent change in MADRS score and the other biomarker measures.

For Aim 3, we will perform logistic regression analyses to evaluate the additive effects of WBC markers of impaired cellular energy regulation and the other biomarker measures, as predictors of remission (or response). Model selection will be performed using LASSO, and area under the receiver operating characteristic curve (AUC) will be used to evaluate the combined predictive potential of the WBC-based and other biomarkers.

Additionally, we will evaluate whether changes in the biomarker levels (for both WBC-based biomarkers and other biomarkers) are associated with clinical response to ketamine, using similar statistical methods to those described for the analysis of baseline biomarkers. Finally, to supplement the traditional regression-based approaches, statistical learning classification approaches, including random forests, will be utilized to predict remission (and response) using the different biomarkers and clinical predictors. These exploratory analyses will develop predictive models that will need to be evaluated in independent samples collected in future studies.

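### No regression model specified in E.16 names diagnosis, although the plan intends a 70/30 unipolar/bipolar mix, so the models cannot show that a marker adds to what diagnosis already tells

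*Combined protocol and SAP*

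**What the plan says.** Section E.16 gives the intended composition of the sample: "The intent is to enroll 100 subjects (70 unipolar/ 30 bipolar) over 4 sites", which it puts at about 25 per site. This is an intention; no quota, cap or stratified enrolment is described. The total rests on feasibility: "The sample size of 100 has been selected based on feasibility of completion across the 7 study sites".

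The models in the same section are as follows.

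- **Aim 1, remitters v non-remitters:** baseline markers are compared "using ANCOVA models adjusted for study site, age, and sex".
- **Aim 1, responders:** "Analyses comparing the baseline biomarkers of responders and non-responders will be performed using similar models".
- **Aim 1, continuous outcome:** "the association of biomarkers with percent change in MADRS score will be evaluated using linear regression mixed models". No covariates are listed.
- **Aim 2:** "For Aim 2, similar analyses will be performed comparing the other biomarker measures between remitters and non-remitters".
- **Change markers:** methods like those for the baseline markers.
- **Aim 3:** logistic regression with LASSO selection, judged by AUC. The only predictors named are the WBC markers and the other biomarkers.
- **Supplementary learning methods, including random forests:** biomarkers plus clinical predictors that are not listed. Diagnosis is neither named nor excluded.

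E.16 has no diagnosis term, interaction, stratified analysis or table by diagnosis. Diagnosis is nevertheless available, because E.5.c has it confirmed with the SCID after consent.

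**The concern.** The trial pools two disorders and looks for blood markers that predict the result of ketamine treatment. Diagnosis is in the chart before any blood is drawn, so a new marker is useful to the extent that it says something diagnosis does not.

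Confounding by diagnosis needs two conditions together: the marker level differs between unipolar and bipolar patients, and so does the remission rate. Then remitters and non-remitters contain different shares of bipolar patients, and their contrast is partly a unipolar/bipolar contrast. Adjustment for site, age and sex does not in general remove this. The same reasoning applies to response, to percent change in MADRS and to the change markers.

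In Aim 3, a proxy for diagnosis could be selected and credited with an AUC that diagnosis alone would give, because no base model is specified for comparison. Such a marker could also replicate in another mixed sample with the same structure, so later validation would not necessarily expose it.

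**Working it through.** **The plan's own figures.** 70 + 30 = 100 and 100/4 = 25 per site, as stated. E.16 gives no power, effect size or significance level, so there is nothing further to reproduce. The 5% two-sided level below is a benchmark chosen for this check.

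**Inputs.** The 70/30 mix is from E.16. The documents give no remission rate or marker level by diagnosis. The two pilot studies in D.1 report pooled remission of 50% (n = 10) and 42% (5 of 12, with 3 bipolar patients). The remission splits and marker shifts below are therefore assumptions, chosen to keep overall remission between 44% and 47%.

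**Size of the induced difference.** Let the marker have no association with remission within either diagnosis, and differ by d SD between diagnoses. Then:

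induced gap = d × [P(bipolar | non-remitter) − P(bipolar | remitter)]

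For remission of 50% unipolar and 30% bipolar:

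- Remitters: 70 × 0.50 + 30 × 0.30 = 35 + 9 = 44. Bipolar share 9/44 = 0.205.
- Non-remitters: 35 + 21 = 56. Bipolar share 21/56 = 0.375.
- Difference in shares 0.170, so d = 0.5, 0.8 and 1.0 give gaps of 0.085, 0.136 and 0.170 SD.

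**False-positive rates.** These come from 8,000 simulated trials per scenario, using a linear model of marker on remission at two-sided 5%, without and with a diagnosis term. Site, age and sex were not simulated.

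| Remission, unipolar / bipolar | Difference in bipolar share | d = 0.5 | d = 0.8 | d = 1.0 |
|---|---|---|---|---|
| 45% / 45% | 0 | 5.0% | 4.9% | 4.8% |
| 50% / 40% | 0.084 | 5.4% | 6.1% | 7.1% |
| 50% / 30% | 0.170 | 6.8% | 9.8% | 12.0% |
| 55% / 25% | 0.254 | 9.4% | 15.8% | 21.9% |

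A normal approximation with mixture variances agrees to within one percentage point (for example 7.0%, 9.8% and 12.1% in the third row). With diagnosis in the model, the rate was 4.7% to 5.3% in every scenario.

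**Scale.** The unadjusted remitter/non-remitter difference detectable with 80% power is (1.96 + 0.84) × √(1/R + 1/(100 − R)). This is 0.57 SD for R = 42 remitters and 0.56 SD for R = 50. The largest induced gap in the table is 0.254 SD.

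**Aim 3.** For a binary predictor, AUC = 0.5 + half the difference in shares. Diagnosis alone would have an AUC of 0.5 + 0.170/2 = 0.585 at 50/30, and 0.5 + 0.254/2 = 0.627 at 55/25.

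**Precision.** Leaving diagnosis out raises the residual variance. Putting it in costs something through its correlation with remission.

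- Equal remission, d = 1.0: residual variance falls from 1 + 0.7 × 0.3 = 1.21 to 1. The standard error falls by 1 − 1/√1.21 = 9%.
- 50/30, d = 0.5: residual variance without the term is 1.051, and the variance inflation with it is 1.035. The standard error falls by 1 − √(1.035/1.051), about 1%.
- 55/25, d = 0.5: the corresponding values are 1.049 and 1.082, so the standard error rises by about 2%.

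Any precision gain is therefore secondary: at most about 9%, and nil or slightly negative where the marker shift is small and the remission gap large.

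**The case against.** The strongest objection is that the key premise is not in the documents. They do not report remission or marker levels by diagnosis, and with equal remission there is no inflation whatever the marker shift. At a 10-point remission gap the inflation is slight. This stands, and it makes the harm conditional.

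Second, Aims 1 to 3 concern prediction in a pooled population of unipolar and bipolar patients, and Hypothesis 1a speaks only of association. A marker that tracks diagnosis would be truly associated with remission in that population if remission differs. This also stands. It narrows the point to whether a marker adds anything beyond diagnosis, which the specified models do not address.

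Third, the simulation omits site, age and sex. Sites choose inpatient or outpatient recruitment (E.5.a), so adjustment for site might absorb part of a diagnostic imbalance. How much is unknown.

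Fourth, the only patient factor that the documents link to ketamine response is concurrent benzodiazepine use (D.1), which the models also leave out. That is fair, but it does not weaken the case for diagnosis, which is the characteristic for which E.16 itself sets out a mix.

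Fifth, section A calls the biomarkers exploratory, and E.16 says the predictive models need evaluation in independent samples. This lowers the stakes without removing the point.

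A reader might infer that the plan fixes the 70/30 split, that every biomarker analysis leaves diagnosis out, or that a marker difference between diagnoses is enough to mislead. The text supports none of these. The split is an intention; the random-forest step could include diagnosis among its unnamed clinical predictors; the percent-change models leave their covariates unstated; and remission must differ as well as the marker.

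**Conclusion.** The point holds in a limited form. No regression model specified in E.16 names diagnosis, although the plan expects a mixed sample and records diagnosis at entry. If marker and remission both differ by diagnosis, the models cannot separate a proxy for diagnosis from a marker that informs beyond it.

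Against a 5% benchmark, the false-positive rate ranges from about 5% (equal remission) to about 22% (55% v 25% with a 1.0 SD marker shift), and a diagnosis term returns it to about 5%. These figures rest on assumed remission rates and marker shifts, on no association within diagnosis, and on a model without site, age and sex. They show what could happen, not what will. It would go too far to conclude that the planned analyses are invalid or that any marker will be falsely reported. This is an inexpensive improvement to exploratory analyses, and the documents do not demonstrate an error.

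**What to change.** Amend E.16 as follows.

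- Add diagnosis (unipolar v bipolar) to site, age and sex in the Aim 1 and Aim 2 ANCOVA models and in the change-marker models. State the covariates of the percent-change mixed models, with diagnosis among them.
- In Aim 3, enter diagnosis unpenalised and report the gain in AUC from the biomarkers over a base model with diagnosis and the other clinical covariates. Without that comparison, an AUC that includes diagnosis would not show what the biomarkers contribute.
- List the clinical predictors for the random forests and include diagnosis.
- Show the marker-remission association separately by diagnosis as a descriptive table. With about 30 bipolar patients, an interaction test would have little power and should not carry the conclusion.

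The cost is one degree of freedom per model and a few sentences of text. No new data are needed.

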## A. BRIEF SUMMARY

This multi-site (Johns Hopkins Hospital, Mayo Clinic (Rochester, MN), Pine Rest Christian Mental Health Services, University of Michigan, and the University of Pennsylvania), open-label, single-arm clinical trial is designed to develop preliminary biomarkers of ketamine response in 100 patients with treatment-resistant non-psychotic unipolar major depression (MDD) or bipolar I or II depression (BPD). Ketamine will be administered intravenously (IV) at a subanesthetic dose of 0.5 mg/kg delivered over 40-minutes or 100-minutes of infusion time. Enrolled subjects will receive a total of three acute phase infusions, delivered at least every other day, within a time window of up to 11 days including the first infusion day. The primary outcome will be remission, as defined by a Montgomery-Åsberg Depression Scale (MÅDRS) score  $\leq 9$ . The secondary outcome measures include reduction of suicidality, as defined by a 50% reduction in the Beck Scale for Suicidal Ideation (BSS). Exploratory biomarkers for ketamine treatment outcome include baseline to endpoint change in WBC stimulated mTOR, AKT, and GSK3 signaling. Additional sample for the ascertainment of other biomarkers will also be taken.

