### **B.7. Hypotheses/Specific Aims**

We will enroll 100 adults with treatment-resistant unipolar or bipolar major depression (TRD) across 8 clinical sites and provide three IV ketamine infusions (0.5 mg/kg, infused over at 40-minutes for first infusion and subsequent infusions at either 40-minutes or 100-minutes) and measure their depressive symptom responses. Biomarkers will be developed using blood samples from study subjects, taken prior to (predictive biomarkers) and following ketamine treatment (change biomarkers). We will begin by studying the predictive value of mTOR target engagement by ketamine using a WBC assay for antidepressive response to ketamine (**Aim 1**); however, samples will be used to develop multiple blood-based biomarkers for ketamine antidepressive effects (**Aim 2**). We will also examine the effect of combining multiple blood-based biomarkers for predicting antidepressive response to ketamine in adults with TRD (**Aim 3**).

Specific to Mayo Clinic-Rochester, a subset of 10 subjects with treatment-resistant unipolar major depression will be enrolled in support of Mayo Clinic IRB # 17-011373, "Central versus Peripheral Glutamate Biomarkers for Treatment Response during a Single Infusion of Intravenous Ketamine for Treatment-Resistant Depression". Subjects will be provided one IV ketamine infusion (0.5 mg/kg, infused over 40 minutes) and will have measured their depressive symptom responses. In this subset of subjects, adults (aged 18-65 years) with treatment-resistant depression will be included. For this subset of subjects, blood draw schedule will defer to those IRB-approved for IRB # 17-011373. Blood samples will be drawn by CRTU staff from the subject before the first ketamine infusion (81ml), during the infusion (1ml at 20 minutes), at infusion stop time (81ml at 40 minutes), and twice after infusion stop time (1ml at 1 hour after the infusion and 1ml at 24 hours after the infusion) for a total of 165ml at Acute Infusion #1. A subject may be eligible to enroll in both trials through trial-specific informed consent forms. If a subject enrolls in both trials, collection of blood samples at Acute Infusion #1 will serve purposes of both trials.

**Aim 1: Determine the effectiveness of a WBC marker of impaired cellular energy regulation (see §B5.c.) as a biomarker for predicting antidepressive response to ketamine in adults with TRD.**

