*Hypothesis 1a: Baseline WBC markers of impaired cellular energy regulation will be associated with measures of clinical response to ketamine (predictive biomarker);*

*Hypothesis 1b: Changes in WBC markers of impaired cellular energy regulation will be associated with clinical response to ketamine (change biomarker).*

**Aim 2: Examine the effectiveness of other blood-based biomarkers with strong potential for predicting antidepressive response to ketamine in adults with TRD.**

For this exploratory aim, we have formed a panel of investigators across multiple sites with experience in the development of biomarkers for severe affective disorders and with the treatment of TRD using IV ketamine (see §B.6., para. 2). These additional biomarkers will be measured using blood samples collected from study participants, and will be correlated with IV ketamine-associated treatment response in order to provide preliminary validation.

**Aim 3: Examine the effectiveness of combining blood-based biomarkers for predicting antidepressive response to ketamine in adults with TRD.**

A similar approach will be taken to develop additional biomarkers that are of interest to project collaborators.

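### Aim 1 asks how well a WBC marker predicts antidepressive response, but no measure of discrimination is planned for any WBC marker on its own

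*Combined protocol and SAP*

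**What the plan says.** Section B.7 states Aim 1 as: "Determine the effectiveness of a WBC marker of impaired cellular energy regulation", and gives its use: "as a biomarker for predicting antidepressive response to ketamine in adults with TRD". Hypothesis 1a, in the same section, is worded as an association but carries a predictive label: "Baseline WBC markers of impaired cellular energy regulation will be associated with measures of clinical response to ketamine (predictive biomarker".

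Section A makes remission the primary outcome: "The primary outcome will be remission, as defined by a Montgomery-Åsberg Depression Scale (MÅDRS) score" of 9 or less.

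Section E.16 plans three analyses of the baseline markers under Aim 1:

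- For remission: "For Aim 1, we will compare baseline WBC markers of impaired cellular energy regulation", with the comparison made "between remitters and non-remitters using ANCOVA models adjusted for study site, age, and sex".
- For response: "Analyses comparing the baseline biomarkers of responders and non-responders will be performed using similar models".
- Linear mixed models relate the markers to percent change in MADRS.

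Logistic regression with remission or response as the outcome appears only under Aim 3, where the WBC markers and the other biomarkers are considered together and selected by LASSO. There the AUC "will be used to evaluate the combined predictive potential of the WBC-based and other biomarkers". Random forests are a supplement, again with several biomarkers plus clinical predictors.

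**The concern.** The aim is about prediction: given a patient's baseline marker, how well can one tell who will respond? Section B.4 gives the clinical purpose, which is to stratify patients by how likely they are to respond. The two group comparisons run the other way. They estimate how far the mean marker differs between outcome groups. The MADRS model gives a slope on a continuous score. None of the three yields an odds ratio for remission or response, an AUC, or a sensitivity and specificity for a WBC marker.

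Aim 3 does not fill the gap. Its AUC describes the selected panel, and LASSO may drop the WBC markers from it.

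At stake is what a positive Aim 1 result would mean. A clear p-value can go with a marker that separates the groups poorly, and the planned output would not show this directly. Table 2 of section E.7.a labels the mTOR/GSK3 marker as primary, so it is the marker for which readers will most want that figure.

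**Working it through.** **Is there a figure to reproduce?** No. Section E.16 sets the sample size of 100 on feasibility and gives no alpha, power, effect size or SD. The figures below are therefore an illustration.

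**Inputs from the document**

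- N = 100 (E.16).
- Pilot remission rates (D.1): 50% in Study 1, and 5 of 12 = 42% in Study 2.

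**Assumptions, not in the document**

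- Two-sided alpha 0.05, and 80% power where power is used.
- Marker normal with equal variance in both groups.
- No dropout; site, age and sex ignored.
- 42 remitters as the central case, 30 to 50 as the range, 20 as a low bound.

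**Step 1. Is the ANCOVA a valid test?** Yes. With the same covariates, the t statistic for remission in a linear model of the marker equals the t statistic for the marker in a linear model of remission, because both depend only on the partial correlation. In one simulated data set of 100 patients with four sites, age and sex, t was 5.38 both ways. The planned test of association is sound, so what is missing is a different quantity.

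**Step 2. Smallest significant difference, in SD units.** d = t(0.975, 98) × √(1/n₁ + 1/n₀). With 42 and 58: 1.984 × √(1/42 + 1/58) = 1.984 × 0.2026 = 0.402.

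**Step 3. Difference detectable with about 80% power.** d = (1.984 + 0.842) × 0.2026 = 0.573.

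**Step 4. Convert to discrimination.** AUC = Φ(d/√2). Sensitivity at 80% specificity = Φ(d − 0.8416).

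- d = 0.402: AUC = Φ(0.284) = 0.612; sensitivity = Φ(−0.440) = 0.330.
- d = 0.573: AUC = Φ(0.405) = 0.657; sensitivity = Φ(−0.269) = 0.394.

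| Remitters of 100 | d just significant | AUC | Sensitivity at 80% specificity | d at about 80% power | AUC | Sensitivity at 80% specificity |
|---|---|---|---|---|---|---|
| 20 | 0.50 | 0.64 | 36% | 0.71 | 0.69 | 45% |
| 30 | 0.43 | 0.62 | 34% | 0.62 | 0.67 | 41% |
| 42 | 0.40 | 0.61 | 33% | 0.57 | 0.66 | 39% |
| 50 | 0.40 | 0.61 | 33% | 0.57 | 0.66 | 39% |

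**Step 5. Precision of the AUC.** With 42 remitters and AUC 0.612, the Hanley-McNeil standard error is 0.0577. The 95% interval is 0.612 ± 1.96 × 0.0577, or 0.499 to 0.725. At AUC 0.657 the standard error is 0.0561 and the interval is 0.547 to 0.767.

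**The case against.** Much of the case for the plan stands.

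- Hypothesis 1a speaks of association, and the planned models test exactly that. A reader might infer that the ANCOVA has the wrong outcome variable or leaves the hypothesis untested. The documents do not support this, and Step 1 shows that the direction of the linear model does not alter the test.
- A reader might infer that Aim 1 yields nothing but a mean difference in the marker. That overlooks the MADRS model, which gives a slope on the clinical scale.
- A reader might infer that a later study would have nothing to plan from. That does not follow. Section E.16 promises means and SDs for most data elements. A standardised difference is itself a planning figure, and it converts to an AUC under normality, as above.
- The aim speaks of response. Remission is the primary outcome and the first grouping analysed, but the gap should not be read as concerning remission alone.
- The work is described as preliminary and exploratory. Section E.16 says the predictive models must be evaluated in independent samples, and no success criterion is set for Aim 1. That a significant result would be presented as predictive success is a risk, not something the plan states.
- Aim 3 and the random forests do model remission with WBC markers among the candidates. Even so, neither isolates a WBC marker.
- The illustration is unadjusted, and adjusted significance does not map exactly to an unadjusted AUC. The 42% comes from 12 inpatients given 100-minute infusions.

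One thing is left standing: the wording of Aim 1 asks about effectiveness for prediction, and no planned output measures that for a WBC marker alone.

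**Conclusion.** The concern holds as an omission. The Aim 1 analyses are valid for association and should stay, but they need a single-marker measure of discrimination beside them if Aim 1 is to answer its own question.

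Under the stated assumptions, with 30 to 50 remitters, a difference that just reaches significance goes with an AUC of about 0.61 to 0.62. With 42 remitters such a marker would miss about two-thirds of remitters at 80% specificity (1 − 0.33 = 0.67). A difference detectable with about 80% power goes with an AUC of about 0.66. A larger true difference would give a higher AUC. The figures show what a p-value alone could conceal; they do not forecast the result.

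**What to change.** In section E.16, Aim 1, add the following for each WBC marker (mTOR, AKT, GSK3):

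1. A logistic model with remission as the outcome and the baseline marker per SD as the predictor, adjusted for site, age and sex. Fit a separate model for response. Use the same remitter and responder definitions as in the ANCOVAs.
2. The odds ratio with its 95% CI.
3. The AUC of the marker alone with its 95% CI. State that this is not the AUC of the model with covariates, which would credit site, age and sex to the marker.
4. A sentence saying that the Aim 1 statement about prediction rests on items 2 and 3, and that the ANCOVAs and the MADRS percent-change model are the association analyses.

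The cost is a change of wording and a little more analysis on the same data, with no added visits or samples. Site terms may be unstable where a site enrols few patients; they can be pooled or penalised, and the rule should be stated in advance. A marker may also look less impressive than its p-value suggests.

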## E.3. Inclusion Criteria

For inclusion in this study, the following are required:

- Ability to provide informed consent;
- Current psychiatric inpatient (voluntary only) or outpatient treatment;
- Male or female;
- Age 18-65 years;
- Meets DSM-5 diagnostic criteria for major depressive disorder, bipolar I disorder, or bipolar II disorder;
- PHQ-9 total score  $\geq 15$  at screening and at baseline (just prior to first acute phase ketamine infusion);
- Treatment-resistant depression, as defined by failure of at least two previous antidepressant or mood stabilizing treatments within the current depressive episode. Failed antidepressant or mood stabilizing treatments can include pharmacotherapy for depression at an adequate dose for at least 8 weeks, or an acute series of at least 6 administrations of electroconvulsive therapy (ECT);
- Ability to pass a comprehension assessment test related to effects of ketamine and trial objectives and criteria.

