#### **E.5.d. Additional screening procedures**

Assessments will also be used to confirm severity of depression and suicidal ideation, and will also serve as baseline scores at initial infusion of study drug. The PHQ-9 will be used to define a threshold score of  $\geq 15$  for enrollment into the study. All qualifying subjects will be administered the Montgomery-Åsberg Depression Scale (MÅDRS) [54] as an additional measure of depressive psychopathology, and the Suicide Status Form (SSF II-R) [55] as a measure of suicide potential. Pregnancy tests will be administered for women  $< 55$  years of age, and urine drug of abuse screens will be reviewed for all participants. The study entry criterion of having failed at least two previous antidepressant or mood stabilizing treatments within the current depressive episode will be assessed using an Antidepressant Treatment History Form (ATHF).

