**Clinical Assessments.**

Mood (MADRS) and suicide measures (BSS) will be obtained by the study coordinator at baseline, at the end of infusion (40-min or 100-min); and at 24 hours post-infusion time. Thus, there will be three clinical outcome assessment times for these measures per infusion. The Snaith-Hamilton Pleasure Scale (SHAPS) will be administered by the study coordinator at baseline, 24 hours following the first infusion, and 24 hours following the third (final) acute phase infusion. An investigator will complete a CGI-Severity of Illness (CGI-S) assessment at baseline before each infusion, and an investigator will complete a CGI-Global Improvement (CGI-C) assessment at the end of each infusion, and at 24 hours post-infusion for each infusion. See §E.8 for description of assessment measures.

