## E.9. Measures

- 9-item Patient Health Questionnaire (PHQ-9):** A self-report screening measure of depressive symptoms, directly correlating with depression symptoms used for diagnosis and widely used in all care settings by all medical specialties [64]. Used only as initial screening into study.
- Depression Module of the SCID:** The Structured Clinical Interview for DSM-IV is a diagnostic exam used in this case to determine depressive disorder diagnoses [67]. The SCID is thus performed to define entry into study.
- Montgomery Åsberg Depression Rating Scale (MÅDRS):** A 10-item clinician rating of depressive symptoms used in the vast majority of previous ketamine research in treatment resistant depression. Each item is scored on a 7-point scale (0 to 6) (range 0–60). Anchors are provided for even numbered scale points. Higher scores represent higher levels of depression. Its psychometric properties have been studied extensively in adults [68]. The MÅDRS in adults has high interrater reliability, with estimates as high as 0.97 between a psychiatrist and general practitioner [18]. Correlation between each item and total score ranges between 0.12 (reduced appetite) and 0.84 (apparent sadness). The MADRS correlates with global ratings (0.70) and the HRSD17 (0.59). The MÅDRS has established scores for varying levels of symptom severity. Scores of 44, 32, 23, 15, and 7 have been suggested to designate very severe, severe, moderate, mild, and recovered depressions, respectively [19]. The scale is unidimensional and not confounded by somatic or psychomotor symptoms [20, 21]. While the MÅDRS does not specify a time frame for rating the symptoms, it is usually used to assess the prior week. Previous analysis has assessed remission scores for depression as  $\leq 9$  using the MÅDRS. Used repeatedly as a measure of depression response and remission criteria [73].

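### The Aim 1 remission ANCOVA omits baseline MADRS, so it cannot show whether a marker is associated with remission beyond a severity score already collected

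*Combined protocol and SAP*

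**What the plan says.** Section E.16 compares baseline white-cell markers "between remitters and non-remitters using ANCOVA models adjusted for study site, age, and sex". The responder comparison and the Aim 2 analyses are to use similar models. The association with percent change in MADRS is to be tested in mixed models whose covariates are not named. Aim 3 (logistic regression, LASSO, AUC) names only biomarkers. Clinical predictors appear once, unlisted, in the supplementary statistical-learning step.

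Section A defines the grouping variable: "The primary outcome will be remission, as defined by a" MADRS of 9 or less. Hypothesis 1a in B.7 reads "Baseline WBC markers of impaired cellular energy regulation will be associated with measures of clinical response to ketamine", while the title of Aim 1 describes the marker "as a biomarker for predicting antidepressive response to ketamine in adults with TRD".

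Baseline severity is available. Section E.6.b states "Mood (MADRS) and suicide measures (BSS) will be obtained by the study coordinator at baseline", and Table 1 schedules MADRS at screening and before infusion 1. Entry is set on PHQ-9 ≥15 (E.3). MADRS is given only "as an additional measure of depressive psychopathology" (E.5.d), so no entry rule narrows the range of baseline MADRS.

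**The concern.** The outcome that forms the groups and the missing covariate are the same scale at two times. With an absolute cut-off, a patient who starts higher must improve by a larger percentage to be called a remitter. Unless sicker patients do improve proportionally more, remitters will have started lower on average, and any marker correlated with severity will then differ between remitters and non-remitters.

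What is at stake is interpretation. Section B.4 wants markers that help clinicians sort patients by likelihood of response. A blood assay that only repeats a rating already taken before infusion 1 does not serve that purpose, and the planned model cannot tell such an assay from one that carries separate information. Aim 2 reuses the same models for many further markers, so the ambiguity would carry into the choice of markers for later studies.

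**Working it through.** **No plan figure to reproduce.** The sample size of 100 rests on feasibility. E.16 gives no effect size, SD, alpha or power.

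**Step 1: what the cut-off demands.** E.9 gives severity anchors: "Scores of 44, 32, 23, 15, and 7 have been suggested to designate very severe, severe, moderate, mild, and recovered depressions, respectively". The percent fall needed to reach 9 is (baseline − 9)/baseline:
- from 23: 14/23 = 60.9%
- from 32: 23/32 = 71.9%
- from 44: 35/44 = 79.5%

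**Step 2: how often a pure severity proxy is flagged.** The documents do not give the marker-severity correlation r, the baseline SD or the baseline-endpoint correlation, so these are assumed. Each simulated trial has 100 complete patients at 4 sites of 25, and baseline MADRS with mean 32 and SD 4, 6 or 8. The marker has correlation r with baseline MADRS and carries no other information. The marker is regressed on remission, site, age and sex (residual df 100 − 7 = 93), then with baseline MADRS added (df 92). There are 4000 replicates per cell; the Monte Carlo standard error is about 0.34 points at 5% and 0.65 at 22%. Three relations between improvement and baseline are used:
- *Independent*: percent improvement has mean 50 or 64 and SD 30, unrelated to baseline. Remission is 26-28% or 42-45%. This isolates the effect of the cut-off.
- *Sicker improve more*: the same, but percent improvement correlates +0.2 with baseline.
- *Linked scores*: endpoint SD 10, baseline-endpoint correlation 0.3 or 0.5, endpoint mean 16 or 11. Remission is 26% or 44%.

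The higher remission rates are near the 42% and 50% of the two pilot studies in D.1.

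Rejection at a nominal 5% with r = 0.3:

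| Scenario | Remission ANCOVA as planned | Percent change without baseline MADRS |
|---|---|---|
| Independent | 5.6-11.1% | 4.8-5.4% |
| Sicker improve more | 5.0-6.0% | 8.8-9.9% |
| Linked scores | 9.6-21.9% | 5.3-19.0% |

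With baseline MADRS added, the remission ANCOVA rejects in 4.0-6.1% throughout and the percent-change model in 4.5-5.5%. At r = 0 the ANCOVA without it holds its level (4.4-5.5%). In the independent scenario, r = 0.2 gives 5.8-7.4% and r = 0.4 gives 6.2-15.0%.

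**Step 3: what drives the linked-scores figures.** The slope of endpoint on baseline is correlation × 10 / baseline SD. It runs from 0.3 × 10/8 = 0.375 to 0.5 × 10/4 = 1.25. Proportional improvement would give 16/32 = 0.50 or 11/32 = 0.34. The slope exceeds that value in 10 of the 12 cells, so most of this scenario also assumes that sicker patients improve proportionally less. The 19.0% for percent change is at SD 4 and correlation 0.5, where the slope is 1.25.

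**Step 4: sensitivity.** A second set of assumptions also keeps improvement independent of baseline: baseline mean 33, SD 5 or 8; mean improvement 70%; remission 45-49%. At r = 0.3 it gives 6.3% and 9.0% when improvement has SD 30 points, and 10.4% and 16.7% when it has SD 15. With baseline MADRS it gives 5.0-5.4%. The less improvement varies between patients, the more baseline decides who remits.

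**Step 5: responder comparison.** E.1 promises a definition of response, but no MADRS threshold is given. If response means a fall of at least 50%, r = 0.3 gives 4.5-5.6% (independent) and 4.9-11.7% (linked scores), against 4.3-5.5% with baseline MADRS.

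**The case against.** The strongest reply is that the plan does what it sets out to do. Hypothesis 1a asks only for association, and a marker that predicts remission partly through severity still predicts it. No passage makes added value over MADRS an Aim 1 objective, so the rejection rates above are false-positive rates only for a null hypothesis that the protocol does not state. This stands, and it is why the model without baseline MADRS should be kept.

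E.16 also has partial safeguards. Percent change is scaled to baseline, the learning step admits clinical predictors, and the predictive models are described as exploratory and needing independent samples. Percent change holds its level when improvement is independent of baseline and is exposed only when percent improvement depends on it. The clinical predictors might include MADRS, but the text does not say so. The exploratory status limits the harm. None of these supplies the severity-adjusted comparison.

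Finally, putting baseline MADRS into an ANCOVA with the marker as outcome tests conditional association. It does not measure gain in prediction. That is correct, and the fix therefore includes a separate model for it.

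**Conclusion.** The omission is real and its consequence is limited. The planned ANCOVA can show that a marker differs between remitters and non-remitters, but not whether it does so beyond baseline MADRS. The cut-off by itself has a modest effect under the main assumptions: about 6-11% at r = 0.3, rising to 17% if improvement varies little between patients. There is none at r = 0 and almost none if sicker patients improve proportionally more. All sizes rest on assumed correlations and SDs. The conclusion does not depend on when remission is assessed.

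A reader might infer three stronger things that the documents do not support:
- *That the Aim 1 test is invalid.* Under Hypothesis 1a a severity-tracking marker is a true association.
- *That the absolute cut-off alone produces the 10-22% of the linked-scores scenario.* Most of those cells add a further assumption, that sicker patients improve proportionally less, and nothing in the documents establishes it.
- *That adjustment would isolate response to ketamine.* In a single-arm trial it cannot separate drug response from general prognosis.

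This is a free improvement, held with medium confidence.

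**What to change.** In E.16:
1. For the Aim 1 and Aim 2 remission and response comparisons, state that the models are adjusted for study site, age, sex and baseline MADRS (score before infusion 1). Report the model without baseline MADRS beside it, and label the two as conditional and overall association.
2. Name the covariates of the percent-change mixed model and include baseline MADRS.
3. To measure added predictive value, report a logistic model for remission with baseline MADRS, site, age and sex, fitted with and without the marker, with a likelihood-ratio test and the change in AUC. This fits the logistic and AUC methods already planned for Aim 3.

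The cost is wording, a little extra analysis and one degree of freedom per model (93 to 92 in the ANCOVA). No new data are needed. If a marker acts through severity its adjusted estimate will shrink, which is why both models should be shown.
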